8.1.3 Analysis of Efficacy

This is a pharmacodynamic and tolerability study of a single administration of P-321 Ophthalmic Solution or Placebo, and therefore, no primary or secondary efficacy endpoints will be formally assessed.

8.1.4 Analysis of Safety

All safety data collected on or after the date that study medication was first dispensed up through the date of the final post dose assessment will be summarized.

The objective of the statistical analysis of the safety parameters is to investigate the data for any effects of study medication on clinical tolerability. All such parameters will be summarized by treatment group and time point as indicated below. Because this study, is a cross over design and, at the cross over treatment, the subjects may no longer be treatment naive, analysis will check for sequence/period effects. If sequence/period effects are detected, the analysis of safety will use just the first period results. Provided that no sequence/period effects are seen, analysis will use the most-recent treatment received as the treatment group.

In the absence of any predefined hypotheses, the general strategy of the safety analysis will be to examine the data summaries for any trends amongst the treatment groups. No formal hypothesis testing will be carried out.

The incidence of AEs will be tabulated by treatment group overall, by treatment sequence, by severity, and relationship to study medication.

Change from baseline values (or shifts from baseline, if more appropriate) will be presented for other safety measures for the visits at which they are assessed.

8.1.5 Interim Reviews of Data

A Data Review Group will review unmasked data when approximately 8 subjects have completed Phase 1. The Data Review Group will include the Principal Investigator (or designee), the Medical Monitor and representative of Parion Sciences not involved in the conduct of the study. Other study site personnel, subjects in the study and those involved in the conduct of the study will remain masked. Additional unmasked reviews of subject data may occur throughout the study to make recommendations on further dose adjustments and for planning purposes. These reviews will follow the procedures outlined in [Section 6.5](#).

8.2 Sample Size Estimation

An initial sample size of approximately 24 subjects is proposed for this study. The study design includes OCT measurements at time 0 (pretreatment) and post dose at 15 minutes, 30 minutes, 1 hour, 2 hours, 4 hours and 6 hours. Shen et al. ([Shen, 2009](#)) reported that among the measures of tear volume and tear film thickness obtainable through OCT, the most sensitive and specific measure of dry eye is the low tear meniscus height (LTMH). Power estimations for a two-period, two-treatment, two-sequence crossover design (2x2x2), this study size when all subjects treated with P-321 are analyzed, will provide 98% power to detect a difference of 60 μm at 1 hour or a power of 99% if the average increase in LTMH over the six hours is 60 μm (assuming within-subject SD of 71). In this study it is expected that the drug will reach its peak effect at 1 hour post dose and that the effect diminishes at hours 4 and 6 (to values still above pre-dose values).

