4 INVESTIGATIONAL PLAN

4.1 Overall Study Design

This is a single-center, randomized, cross-over, placebo-controlled, Phase 2a trial designed to evaluate the pharmacodynamic effects of tear volume of P-321 Ophthalmic Solution in tear-deficient dry eye subjects. Approximately 24 eligible subjects will complete the study which consists of two Phases: Approximately 8 subjects participating in Phase 1 will receive 0.017% P-321 ophthalmic Solution and Placebo, and the remainder of the 24 subjects participating in Phase 2 will receive either 0.05%, 0.017% or 0.01% P-321 and placebo. The decision on the dose administered in Phase 2 will be made following unmasked data review from subjects in Phase 1. In each Phase, subjects will receive sequentially two treatments: P-321 Ophthalmic Solution (Treatment A) and Placebo (Treatment B). Subjects will be randomly assigned to receive treatment sequence AB or BA, in a 1:1 ratio.

The pharmacodynamic measures of tear volume will be assessed by two methods: UHR-OCT and Keratograph 5M. Optical coherence tomography (OCT) has been used to image the anterior segment of the eye including tears on the ocular surface. The method is non-invasive and non-contact which is suitable for imaging the tear meniscus around both upper and lower lids. The system at Bascom Palmer Eye Institute is a custom made OCT system (UHR-OCT) with an ultra-high resolution (3 μ m). Many previous studies have been done using UHR-OCT and its clinical application has been well documented. With the wide scan of the UHR-OCT, cross-sectional images of the tear menisci can be imaged and tear meniscus volume can be calculated. The Keratograph 5M is a corneal topographer with a built in camera optimized for external imaging. The Keratograph 5M has a feature that enables the non-invasive assessment of the tear meniscus height of the inferior eyelid from high resolution images obtained under infrared light. With the use of a built-in measurement tool the height of the tear meniscus is obtained.

The study will consist of three study visits: a Screening Visit (Visit 1), and two treatment visits (Visit 2 and Visit 3). The duration of the study may be up to 23 days.

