5 SELECTION AND WITHDRAWAL OF SUBJECTS

5.1 Subject Inclusion Criteria

Subjects must meet the following criteria at Screening to be enrolled in the study:

1. Provide written informed consent
2. Male or female subjects aged 18 to 80 years
3. Are willing and able to follow instructions and can be present for the required study visits for the duration of the study
4. Have a history of predominantly tear-deficient dry eye of mild to moderate severity, in both eyes, supported by a previous clinical diagnosis
5. Subjects must have in at least one eye an average tear meniscus height (TMH) of the lower eye lid of 210 μm or less as assessed by UHR-OCT
6. Have normal lid anatomy
7. Female subjects of child bearing potential must have a negative serum pregnancy test at Screening and agree to use a medically acceptable form of birth control (e.g., intrauterine device, birth control pill, patch or subcutaneous implant, condoms, diaphragm, or abstinence) throughout the duration of the study. Females who are breast feeding an infant are not eligible to participate in the study.
8. Subjects must:
 - a. Remain on current medications for the duration of the study
 - b. Be on the current medication regimen at least during the past 28 days
 - c. Be able to withhold ocular topical medications, including artificial tears, topical steroids, Restasis[®], Xiidra[®], autologous serum, and lid wipes and scrubs on visit days while in the clinic, and for at least 6 hours after dosing with study medication
 - d. If they are contact lens wearers, be able to withhold wearing contact lenses on visit days, while in the clinic, and for at least 6 hours after dosing

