8.1.2 Pharmacodynamic parameters

UHR-OCT will assess the following parameters in both eyes: UTMH, LTMH, UTMV, LTMV, and TTMV (UTMV + LTMV). Treatment group differences for tear volume assessments will be conducted via comparisons of tear meniscus height, and if applicable, tear meniscus volume (TMV). These parameters will be compared between each dose of P-321 Ophthalmic Solution and Placebo using a t-test for study eyes, and for all eligible eyes. Analysis of covariance (ANCOVA) models will be used to adjust for the baseline TMH and TMV for study eyes. For all eligible eyes, a generalized estimation equations (GEE) will also be used to account for the correlation between eyes. For the GEE analysis, an exchangeable correlation matrix will be assumedArea under the curve (AUC) analysis will also be performed as an exploratory analysis to compare OCT assessments and Keratograph 5M LTMH for Placebo vs each dose of P-321.

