8.1.2 Pharmacodynamic parameters

UHR-OCT will assess the following parameters in both eyes: UTMH, LTMH, UTMV, LTMV, and TTMV (UTMV + LTMV). These assessments, as appropriate, will be compared between each dose of P-321 Ophthalmic Solution and Placebo using a t-test for each eye separately and for the within-subject average. Analysis of covariance (ANCOVA) models will be used to adjust for the baseline tear volume and tear meniscus height for each eye separately and for the average of the two eyes. Generalized estimation equations (GEE) will also be used to account for the correlation between eyes. For the GEE analysis, an exchangeable correlation matrix will be assumed. Area under the curve (AUC) analysis will also be performed as an exploratory analysis to compare OCT assessments and Keratograph 5M LTMH for Placebo vs each dose of P-321.

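### The 98% and 99% power figures do not follow from the stated inputs: 24 subjects, 60 µm and a within-subject SD of 71 give about 80% with one value per subject per period

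*Combined protocol and SAP*

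**What the plan says.** Section 8.2 gives the size: "An initial sample size of approximately 24 subjects is proposed for this study". For a two-period, two-treatment, two-sequence crossover it then states that "this study size when all subjects treated with P-321 are analyzed, will provide 98% power to detect a difference of 60" (in µm, for the 1-hour value), with 99% quoted if the six-hour average increase is 60 µm. One SD is given for both, in parentheses after the six-hour clause: "assuming within-subject SD of 71". No source is cited for 71, and the unit to which it applies (study eye, any eye, average of two eyes) is not stated. The synopsis repeats the statement.

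Other parts of the current version that bear on the calculation:

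- Section 4.1: "Subjects will be randomly assigned to receive treatment sequence AB or BA, in a 1:1 ratio", so 24 subjects means 12 per sequence.
- Section 8.3 sets the significance level at 0.05 without saying one- or two-sided.
- Section 8.1.2: tear parameters are "compared between each dose of P-321 Ophthalmic Solution and Placebo using a t-test for study eyes, and for all eligible eyes". It adds: "For all eligible eyes, a generalized estimation equations (GEE) will also be used to account for the correlation between eyes".
- Section 5.4 defines one study eye per subject.
- Section 5.1: "Subjects must have in at least one eye an average tear meniscus height (TMH) of the lower eye lid of 210" µm or less. The synopsis still describes the requirement as applying to both eyes.

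The power statement is word for word that of Version 1.0. There, Section 8.1.2 compared treatments "using a t-test for each eye separately and for the within-subject average", and Section 5.1 required both eyes to qualify.

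**The concern.** A power figure should be recoverable from the inputs printed beside it. Here the sample size, design, difference, SD and significance level are all given, yet the direct calculation falls about 18 percentage points short of 98%.

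The gap is close to a factor of √2 in the standard error. That is what results when an SD of differences is labelled as a within-subject SD, or when the number of independent units is doubled. The first would be a labelling slip that leaves the power intact. The second would overstate the power.

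A reader cannot tell which applies. Power for 60 µm could therefore lie anywhere from about 80% to about 98%. Anyone who later reuses 71 as a within-subject SD may also be starting from a mislabelled number.

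**Working it through.** **Inputs.** N = 24 (Section 8.2); 12 per sequence (Section 4.1); difference 60 µm and SD 71 (Section 8.2); alpha 0.05 (Section 8.3). Two-sided testing is assumed unless stated. Power comes from the noncentral t distribution with noncentrality 60/SE.

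**Step 1: try to reproduce 98% from the inputs as labelled.** With one value per subject per period and within-subject SD 71:

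- SD of the within-subject difference = 71 × √2 = 100.4
- SE = 71 × √(2/24) = 20.50
- noncentrality = 60/20.50 = 2.93, with 24 − 2 = 22 df
- power = **79.9%** two-sided, 88.3% one-sided

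A simple paired t-test (23 df) gives 80.0%. The normal approximation gives 83.3% two-sided and 90.0% one-sided. None of these is 98%.

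**Step 2: find readings that do give about 98%.**

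| Reading | SE | df | Power, two-sided |
|---|---|---|---|
| 71 is the SD of the P-321-minus-placebo difference | 71/√24 = 14.49 | 22 | 97.7% |
| 48 independent units (both eyes of 24 subjects, or 24 subjects per sequence) | 71 × √(2/48) = 14.49 | 46 | 98.2% |
| Average of two eyes, errors uncorrelated | (71/√2) × √(2/24) = 14.49 | 22 | 97.7% |

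All three have the same SE, so the 98% alone cannot tell them apart.

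**Step 3: test the eye-based readings against between-eye correlation.** If 71 is the eye-level within-subject SD and ρ is the between-eye error correlation, the two-eye average has SD 71 × √((1+ρ)/2) and SE equal to that SD × √(2/24), with 22 df. The documents give no ρ, so the values below are assumptions.

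| ρ | SE | Power |
|---|---|---|
| 0 | 14.49 | 97.7% |
| 0.3 | 16.52 | 93.4% |
| 0.5 | 17.75 | 89.8% |
| 0.8 | 19.44 | 83.9% |
| 1 | 20.50 | 79.9% |

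**Step 4: the 99% figure.** It rests on the same 60 µm and the only SD given. As labelled it is again 79.9%. With 71 as the SD of the difference it is 97.7% two-sided. One-sided, that reading gives 99.1%, but it would then give 99.1% at 1 hour too, not 98%. Different powers at the same difference, sample size and test need different SDs, and only one SD is reported.

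**Step 5: what the label would imply if it is right for the study eye.** A power of 98% would need a difference of about 86 µm with 24 subjects, or 48 subjects for 60 µm. Equivalently, 98% with 24 subjects and 60 µm needs a within-subject SD of about 49.4, close to 71/√2 = 50.2.

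**The case against.** The strongest reply is that 98% may be correct and only the label wrong. Reading 71 as the SD of the paired difference gives 97.7%, which rounds to the stated figure with no change to size or design. This stands as a live possibility. The printed text would still be wrong, because it calls 71 a within-subject SD, and the 99% would still need its own input.

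A second reply is that counting eyes is part of the plan. That is right as far as it goes. Section 8.1.2 plans a t-test for all eligible eyes, with the GEE in addition, and the synopsis still speaks of both eyes. A reader might infer that the plan excludes an eye-level analysis; it does not. The weakness of the 48-eye reading lies elsewhere. It ignores the between-eye correlation that the GEE is there to handle, and it needs both eyes eligible in all 24 subjects when Section 5.1 asks for only one. The alternative way to reach 48, 24 subjects per sequence, conflicts with a total of about 24 split 1:1.

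Third, the SD follows the six-hour clause, so it may not govern the 1-hour figure. That would leave the 98% with no stated SD and would not explain the 99%.

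Fourth, little depends on the number. Section 8.1.3 formally assesses no efficacy endpoint, and the dose-selection criteria use no power threshold. This limits the weight of the point, but does not make the figures agree.

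**Conclusion.** The point holds as an inconsistency between stated inputs and stated output. As labelled, with one value per subject per period and two-sided 0.05, power for 60 µm is 79.9%, against 98% and 99% in the text. One-sided testing raises it only to 88.3%.

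A reader might infer that the study really has only 80% power. The documents do not support that. They do not show where 71 came from or which unit was analysed, and one plausible reading leaves about 98% intact.

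A reader might also take the figure as misleading about individual doses. The power sentence says openly that it covers all P-321 subjects together, so pooled versus per-dose comparison is a separate matter and no part of this discrepancy.

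The result rests on the noncentral t calculation for a 2×2 crossover with 24 completers. The two-eye figures also rest on assumed correlations. The correction concerns a planning figure and does not invalidate the design.

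**What to change.** Trace the source of 71 and the unit used in the calculation, then amend Section 8.2 and the synopsis:

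- (a) If 71 is a true within-subject SD for the study eye, restate the 1-hour power as about 80%.
- (b) If 71 is the SD of the P-321-minus-placebo difference, relabel it (within-subject SD about 50) and keep about 98%.
- (c) If eyes, or 24 subjects per sequence, were counted, recompute for 24 subjects with a stated between-eye correlation and a stated number of eligible eyes. For the latter, the synopsis and Section 5.1 must be reconciled on whether one or both eyes must qualify.

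In every case, give the SD used for the six-hour average and recompute the 99% from it. State in Section 8.3 whether tests are one- or two-sided.

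The cost is a source check, a short recalculation and wording in Section 8.2, Section 8.3 and the synopsis. It needs no additional subjects and no change to procedures. The stated power may become less favourable.

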8.3 Level of Significance

Each hypothesis will be tested at a significance level of 0.05.

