4.2 Endpoints

4.2.1 Primary Endpoint

The primary endpoint for this study is the change in measurements of tear volume over time as measured by the UHR-OCT following the administration of P-321 Ophthalmic Solution and Placebo in subjects with tear deficient dry eye disease.

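### The primary endpoint names no parameter, time point or summary, and every comparison is tested at 0.05 with no order or adjustment, so its false-positive rate is undefined and above 5%

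*Combined protocol and SAP*

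**What the plan says.** Section references are to the current version of the protocol, the one that opens with a summary of changes.

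- Section 4.2.1 defines the primary endpoint as "the change in measurements of tear volume over time as measured by the UHR-OCT" after P-321 and placebo. It names no parameter, time point or summary over time.
- Section 8.1.2 lists what the instrument yields: "UHR-OCT will assess the following parameters in both eyes: UTMH, LTMH, UTMV, LTMV, and TTMV (UTMV + LTMV"). Treatment differences are to be examined through "comparisons of tear meniscus height, and if applicable, tear meniscus volume (TMV"). Each dose is compared with placebo by t-test in study eyes and in all eligible eyes. ANCOVA is added for study eyes and GEE for all eligible eyes. Only the AUC analysis is labelled exploratory.
- Section 8.2 lists six post-dose times (15 and 30 minutes, 1, 2, 4 and 6 hours). It reports a literature finding that "the most sensitive and specific measure of dry eye is the low tear meniscus height (LTMH"). With all P-321 subjects analysed together, it gives 98% power for 60 μm at 1 hour, or 99% if the average increase in LTMH over six hours is 60 μm. It calls neither one primary.
- Section 8.3 reads in full: "Each hypothesis will be tested at a significance level of 0.05". Sidedness is not stated.
- Section 8.1.3 says that "no primary or secondary efficacy endpoints will be formally assessed", because this is a pharmacodynamic and tolerability study.

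**The concern.** A significance level and a power figure have meaning only for a defined claim. Here the named primary endpoint can be read as any of 6 to 30 comparisons for one dose, one eye set and one method. Nothing says which comparison decides or how several are combined. If one favourable p-value among them were reported as the primary result, the 0.05 of Section 8.3 would not describe the chance of a false finding, and the power of Section 8.2 would not describe the chance of a true one.

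The choice is also exposed to the data. The Data Review Group, which includes the Principal Investigator (or designee), the Medical Monitor and sponsor representatives, sees unmasked tear-volume results after about 8 subjects. Section 8.1.5 allows further unmasked reviews throughout the study. With no comparison fixed in advance, the one to emphasise could be chosen after results are known.

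**Working it through.** **1. The plan's own power figure.** Inputs from Section 8.2: n = 24, difference 60 μm, SD 71. Two-sided 0.05 is assumed. If 71 is read as the SD of the P-321 minus placebo difference, the noncentrality is 60/71 × √24 = 4.14. Power is 98.5% by the normal approximation, Φ(4.14 − 1.96), and 97.7% by the t-test with 22 df. This reproduces the stated 98%. If 71 is instead a within-subject SD, as it is labelled, the SD of the difference is 71√2 = 100.4 and power is 79.9% (t) or 83.3% (normal). That is a separate matter. The figures below for the cost of alternatives use the reading that reproduces the plan.

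**2. Number of tests, one dose, one eye set, one method.**
- LTMH only: 1 × 6 times = 6
- Upper and lower heights: 2 × 6 = 12
- All five parameters: 5 × 6 = 30, where TTMV is the sum of two others

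Section 8.1.2 commits to heights and makes volumes conditional, so 30 is not the minimum.

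**3. Chance of at least one two-sided p < 0.05 with no drug effect.**
- Independent tests: 1 − 0.95^k.
- Equal correlation ρ between all tests (normal limit, c = 1.96): 1 − ∫ φ(u) [Φ((c − √ρ u)/√(1−ρ)) − Φ((−c − √ρ u)/√(1−ρ))]^k du, checked by simulated paired t-tests with n = 24.
- Structured simulation: 24 paired differences with mean zero, a common correlation of 0.3 to 0.8 between parameters and between times, TTMV formed as the sum of the two volumes, 23 df, 20,000 trials per scenario.

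| Tests | Independent | Equal ρ = 0.3 | ρ = 0.5 | ρ = 0.8 | Structured, 0.8 to 0.3 | Structured, favouring P-321 only |
|---|---|---|---|---|---|---|
| 6 | 26.5% | 24% | 21% | 14% | 14–25% | 7–13% |
| 12 | 46.0% | 40% | 32–33% | 19–20% | 21–43% | 12–23% |
| 30 | 78.5% | 66–67% | 51–52% | 26–27% | 30–67% | 15–39% |

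The structured and equal-correlation columns differ a little because, in the structured model, tests that differ in both parameter and time are less correlated than tests that differ in only one. A second eye set, a second method or a second dose would add tests that this table leaves out.

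**4. What naming one comparison does.** One test at 0.05 has a 5% error rate and keeps the 97.7%. For comparison, with n = 24 and 71 as the SD of the difference:
- both Section 8.2 candidates at 0.025 each: 95.1%
- Bonferroni over six times (0.05/6 = 0.0083): 87.9%
- Bonferroni over 30 tests (0.05/30 = 0.00167): 70.2%

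**5. Pooled or per dose.** The power in Section 8.2 holds when all P-321 subjects are analysed together. If Phase 2 uses a different strength, the dose groups are about 8 and 24 − 8 = 16. On the same reading, per-dose power at 0.05 is 51.8% and 88.1%. Section 8.1.2 compares each dose separately, so the two sections describe different comparisons.

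**The case against.** The strongest reply is that this is a single-centre phase 2a pharmacodynamic study of about 24 subjects. Section 8.3 claims 0.05 only for each hypothesis, which is correct test by test. No section claims family-wise control or states a rule for meeting the primary endpoint, and the dose-selection criteria set no p-value threshold. All of this stands and keeps the severity down. It does not supply a primary comparison. The plan marks only AUC as exploratory, and it disclaims formal testing only for safety (Section 8.1.4).

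Four stronger readings are tempting and are not supported:

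- A reader might infer that the plan has a false-positive rate of 30–67%. That range needs all 30 tests and assumed correlations of 0.3 to 0.8. The documents give no correlations and make volumes conditional.
- A reader might infer that the plan lets any one significant test count as success. No section says so. It is a possibility left open, not a written rule.
- A reader might infer that Section 8.2 already fixes LTMH at 1 hour. It gives two alternatives, and the six-hour average arguably fits the words over time and the duration-of-action objective better.
- A reader might infer that Section 8.1.3 rules out formal assessment of every endpoint. It refers to efficacy endpoints and can be read as leaving the pharmacodynamic endpoint alone. It still sits awkwardly beside a named primary endpoint, a power calculation and an alpha.

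**Conclusion.** The point holds as a defect of specification with a consequence for error control. The primary endpoint has no defining comparison, all tests are at 0.05, and nothing orders or adjusts them. Any reading with more than one test gives a false-positive rate above 5%. Its size depends on assumptions: about 14–25% for LTMH alone at six times, 21–43% for two heights, and 30–67% for all five parameters. These figures assume two-sided tests, correlations of 0.3 to 0.8, 24 subjects, one dose, one eye set and one method. Roughly half of each applies if only results favouring P-321 count. The change should be made, but severity is modest given the phase and purpose of the study.

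**What to change.** In Sections 4.2.1, 8.1.2 and 8.3, name one primary comparison taken from Section 8.2: UHR-OCT LTMH in the study eye, P-321 (all doses pooled, as in the power statement) minus placebo, two-sided 0.05. State one summary, either 1 hour (the expected peak) or the six-hour average, and one of the methods already listed for study eyes. If the average is chosen, say how it is formed and how it relates to the exploratory AUC. Settle this before any unmasked review.

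Label all other parameters, times, per-dose comparisons, eye sets and methods as supportive, with nominal p-values. Clarify in Section 8.1.3 that it refers to clinical efficacy endpoints and not to the pharmacodynamic primary endpoint.

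The cost is wording only: no extra subjects or measurements, no split of alpha and no loss of the stated power. The downside is that a signal at another time, in another parameter or at a single dose can be reported only as supportive.
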